### 5.6.1 Extent of Exposure

Exposure to study drug H3B-6545 will be summarized descriptively, including the following parameters defined per subject:

- Duration of treatment (in month), defined as (date of last dose – date of first dose +1)/30.4375, regardless of drug interruptions.
- Number of cycles received
- Total dose received (mg)
- Actual Dose Intensity (ADI, mg/day), defined as total dose received (mg)/ duration of treatment (days)

In addition, number of patients with dose reduction and dose interruption will be summarized.

A dose reduction refers to the situation when the administration of H3B-6545 was reduced one level lower. Dose interruptions are identified by 0 doses which are preceded and followed by the same dose level. If the dose after the 0 dose is lower than that before the 0 dose, this dose change will be counted as a dose reduction.

A by-patient listing of the date of study drug administration and the dose administered will be presented. Patients experiencing any dose modification (increase, reduction, or interruption), together with the reasons for dose modification, will also be provided in a separate listing.

### 5.6.2 Adverse Events

#### 5.6.2.1 Dose Limiting Toxicity Data

In the Dose Evaluable Set, the number (percentage) of patients with DLTs will be presented by starting dose levels for Phase 1 subjects (100 mg, 200 mg, 300 mg, 450 mg and 600 mg).

A listing of patients with DLTs will be provided. Identifiers for AEs associated with each DLT will be noted in the listing.

### 5.6.2.2 AE Data

Adverse events (AEs) will be collected for each subject until 28 days after last study drug administration. The NCI CTCAE v4.03 will be used for AE reporting.

The AE verbatim descriptions (investigator terms from the CRF) will be classified into standardized medical terminology using the Medical Dictionary for Regulatory Activities (MedDRA). Adverse events (AEs) will be coded to the MedDRA (version 19.1 or higher) lower level term (LLT) closest to the verbatim term. The linked MedDRA PT and primary system organ class (SOC) will also be captured in the database.

A treatment-emergent adverse event (TEAE) is defined as:

- An AE that emerged during treatment (from first dose of study drug up to 28 days after last dose), having been absent at pretreatment (Baseline) or
- Reemerged during treatment, having been present at pretreatment (Baseline) but stopped before treatment, or
- Worsened in severity during treatment relative to the pretreatment state (Baseline), when the AE was continuous.

The AEs will be summarized using the Safety Analysis Set. Only those AEs that were treatment-emergent (TEAE) will be included in summary tables. The incidence of TEAEs will be reported as the number (percentage) of subjects with TEAEs by SOC and PT. A patient will be counted only once within a SOC and PT, even if the patient experienced more than 1 TEAE within a specific SOC and PT. The number (percentage) of patients with TEAEs will also be summarized by maximum NCI CTCAE v4.03 grade, and by causal relationship to study drug (Yes [related] and No [not related]).

Number (percent) of subjects will be summarized by treatment groups in the following analysis:

- Overview of TEAEs (including TEAEs, TEAEs by maximum grade, TEAEs by relationship, treatment-emergent SAEs, treatment-related TEAEs, TEAEs leading to study drug discontinuation, TEAEs with Grade  $\geq 3$ , TEAEs leading to study drug reduction, TEAEs leading to study drug interruption, TEAEs leading to death)
- TEAEs by SOC and PT
- TEAEs by SOC, PT and maximum grade
- TEAEs by PT
- TEAEs of Grade  $\geq 3$  by SOC and PT
- Treatment-related TEAEs by SOC and PT
- Treatment-related TEAEs by SOC, PT and maximum grade
- Treatment-related TEAEs of Grade  $\geq 3$  by SOC and PT

- Treatment-emergent SAEs by SOC and PT
- Treatment-emergent SAEs by SOC, PT and maximum grade
- Treatment related treatment-emergent SAEs by SOC and PT
- TEAEs leading to study drug discontinuation by SOC and PT
- TEAEs leading to death by SOC and PT
- TEAEs leading to study drug reduction by SOC, PT and maximum grade
- TEAEs leading to study drug interruption by SOC, PT and maximum grade

[figure not shown]
Summary of death will be provided with number (percent) of subjects who died during study treatment period or after study treatment. Details concerning patients who died will be listed.

In addition, the following patient data listings will be presented:

- Listing of AEs associated with DLT
- Listing of AEs leading to discontinuation from study drug
- Listing of SAEs
- Listing of all AEs

As exploratory subgroup analysis, the following analysis will be performed by *ESR1* mutation groups or by PgR status:

CCI

#### 5.6.2.3 AE of special interest

Hy's law is the only reportable AESI for this protocol and events of Hy's law will be reported and captured in AE summary table ([Section 5.6.2.2](#)). Potential Hy's law cases will be listed ([Section 5.6.3](#)) and discussed in the clinical study report (CSR).

#### 5.6.2.4 Grouping of AEs

Selected grouped terms will be defined by using coded terms, based on the MedDRA version used at the time of database lock. Grouped AEs will be summarized by treatment groups.

The grouped term "Bradycardia" is defined by PT of "Sinus bradycardia" and "Bradycardia".

### 5.6.3 Laboratory Values

Laboratory results will be summarized by treatment groups on the safety analysis set. The analysis will include assessment collected at baseline and/or during treatment (from first dose to 28 days after last dose date), using Système International (SI) units, as appropriate. Values that are non-missing and reported as ‘below the detectable limit’ of an assay will be replaced by half of the detectable limit in the summary tables.

For all quantitative parameters, the numeric value and the change from baseline to each post-baseline visit (including end of treatment visit and safety follow up visit) will be summarized by visit using descriptive statistics. Qualitative parameters summarized by frequencies (number and percentage of subjects) at each post-baseline visit (including end of treatment visit and safety follow up visit) will be reported.

Furthermore, the frequency of laboratory abnormalities by maximum post-baseline CTCAE grade will be summarized for selected laboratory parameters, including hemoglobin, White Blood Cell Count (WBC), Absolute neutrophil count (ANC), lymphocytes, platelet count, alkaline phosphatase (ALP), aspartate aminotransferase (AST), alanine aminotransferase (ALT), bilirubin, creatinine, estimated glomerular filtration rate (eGFR, calculated using the Modification of Diet in Renal Disease [MDRD] formula), thyroid-stimulating hormone (TSH) and electrolytes. Shift tables will also be produced for selected parameters based on the baseline CTCAE grade and the maximum CTCAE grade at post-baseline visits.

Listings of laboratory results will be provided. In addition, a listing of potential Hy’s law cases will be provided, including subjects who meets one of the following criteria at any post-baseline timepoint (not necessarily at the same timepoint): (aspartate aminotransferase or alanine transferase) $>3 \times$  upper limit of normal (ULN). Parameters (AST, ALT, Total Bilirubin, ALP as multiples of ULN) at all timepoints will be included. Subjects meeting Hy’s Law definition will be discussed in the CSR based on FDA “Guidance for Industry Drug Induced Liver Injury: Premarketing Clinical Evaluations, July 2009”.

### 5.6.4 Vital Signs

By-timepoint analysis: descriptive statistics for vital signs parameters (ie, systolic and diastolic blood pressure [BP], pulse/heart rate [HR], respiratory rate [RR], temperature and weight) during the treatment period and changes from baseline will be summarized by visit, presented by treatment groups on the Safety Analysis Set.

Categorical analysis: the number (percentage) of subjects who meet the criterion ([Table 3](#) and [Table 4](#)) with at least 1 post-baseline result during the treatment period will be summarized (based on worst post-baseline results), and presented by treatment groups:

Blood pressure will also be summarized using a shift table from baseline to worst post-baseline by categories defined based on CTCAE grades.

**Table 3 Blood Pressure Grades**

Grade	Blood Pressure (mm Hg)	
	Systolic	Diastolic
0 (Normal)	$\leq 119$	$\leq 79$
1 (Prehypertension)	120 – 139	80 – 89
2 (Stage 1 Hypertension)	140 – 159	90 – 99
3 (Stage 2 Hypertension)	$\geq 160$	$\geq 100$

For each subject at each visit, systolic blood pressure (SBP) and diastolic blood pressure (DBP) will be graded separately. Then the blood pressure grade will be the worst of the two grades: SBP grade and the DBP grade. The worst blood pressure category per subject during treatment will be used in the shift table.

**Table 4 Criteria for Categorical Analysis of Vital Sign Parameters**

Parameter	Criteria
Heart rate increase	Changes reflecting a more than 25% increase from baseline to a HR > 100 bpm
Heart rate decrease	Changes reflecting a more than 25% decrease from baseline to a HR < 50 bpm

Bpm = beats per minute, HR = heart rate.

A listing of vital sign measurements will be provided.

### 5.6.5 Electrocardiograms

#### 5.6.5.1 Continuous 24-hour Holter Data

For Phase 1 subjects, the effects of H3B-6545 on cardiovascular re-polarization will be evaluated via a 12-lead continuous Holter. On Cycle 1, Day 1 and Day 15, monitoring via Holter will begin at least 1 hour prior to dose and continue through at least 24 hours post dose. The analysis of QT intervals corrected using Fridericia's method (QTcF) and other ECG parameters, and exposure-ECG modeling are documented in a separate analysis plan prepared by ERT.

#### 5.6.5.2 Central and Local 12-lead ECG Data

In addition, central triplicate 12-lead ECG are collected at screening, and on Day 1 and Day 15 of Cycle 1 (for Phase 2 subjects), Day 1 of Cycle 2, 3, and 4 (predose and 3 hours postdose), as well as at the End of Treatment (EOT) visit.

Local 12-lead ECG data maybe collected at scheduled visits starting from Cycle 5 until the last cycle prior to the EOT visit, and at unscheduled visits as clinically required.

For each ECG parameter (QTcF, PR, etc), the average of triplicate at each timepoint (screening, predose and post dose on Day 1 of Cycle 1, 2, 3, 4, EOT, unscheduled, etc) will be used in ECG analysis below:

- By-timepoint analysis: ECG parameters numerical results and changes from baseline at each scheduled timepoint (including EOT and safety follow up visit) during the treatment period will be summarized by treatment groups.
- Categorical analysis: the number (percentage) of subjects who meet the following criterion with at least 1 post-baseline ECG result during the treatment period will be summarized (based on worst post-baseline results) and presented by treatment groups:

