## 5 STATISTICAL METHODS

As of CCI the RP2D of H3B-6545 has been determined as CCI

Three sets of analysis will be performed, including subjects from both Phase 1 and Phase 2 portions of the study, which also includes subjects enrolled under Amendment 06.

Presentation by treatment group: grouping by starting dose levels will be applied to all analyses, unless specified otherwise. The default analysis set is full analysis set (**FAS**, [defined in Section 5.2.1](#)) for all analysis, and response evaluable set (**RES**, [defined in Section 5.2.1](#)) will be applied to selected analysis of response rate.

Presentation by baseline *ESR1* mutation groups: grouping by *ESR1* mutation groups (per sponsor approved laboratory analysis of cfDNA) will be applied to selected efficacy and safety analysis. The default analysis set is FAS subjects who started on CCI with known *ESR1* status.

For presentation by baseline *ESR1* mutation groups, the following definitions are used to define the mutation groups per sponsor approved laboratory analysis of cfDNA, only including subjects with known *ESR1* status:

- **Clonal Y537S** consists of all subjects who receive at least 1 dose of study drug, carry *ESR1* Y537S at a mutation AF  $\geq 0.5\%$ , and do not carry *ESR1* D538G at an AF  $\geq 0.5\%$ .
- **Clonal D538G** consists of all subjects who receive at least 1 dose of study drug, carry *ESR1* D538G at an AF  $\geq 0.5\%$ , and do not carry *ESR1* Y537S at an AF  $\geq 0.5\%$ .
- **Clonal Y537S or clonal D538G** consists of all subjects who are either clonal Y537S or clonal D538G, defined above.
- **Polyclonal Y537S and D538G** consists of all subjects who receive at least 1 dose of study drug and carry both *ESR1* Y537S at an AF  $\geq 0.5\%$  and *ESR1* D538G at an AF  $\geq 0.5\%$ .
- **Y537S and D538G negatives** consists of all subjects who receive at least 1 dose of study drug and carry neither *ESR1* Y537S at an AF  $\geq 0.5\%$  nor *ESR1* D538G at an AF  $\geq 0.5\%$ .

All descriptive statistics for continuous variables will be reported using mean, standard deviation (StD), median, the first quartile (Q1), the third quartile (Q3), minimum and maximum. Categorical variables will be summarized as number (percentage) of subjects. In addition, all data will be presented in subject data listings unless otherwise specified.

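### Table 5 takes the worst post-baseline ECG by starting dose over unequal schedules, which favours higher outlier rates in the 450 mg column

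*SAP*

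**What the plan says.** **Cycle 1 schedule.** SAP Section 5.6.5.2: "central triplicate 12-lead ECG are collected at screening, and on Day 1 and Day 15 of Cycle 1 (for Phase 2 subjects").

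**Later schedule, with no phase limit.** The same sentence continues with "Day 1 of Cycle 2, 3, and 4 (predose and 3 hours postdose), as well as at the End of Treatment (EOT) visit". Local ECGs may follow from Cycle 5, and unscheduled ones as clinically required.

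**Phase 1 in Cycle 1.** Section 5.6.5.1: "For Phase 1 subjects, the effects of H3B-6545 on cardiovascular re-polarization will be evaluated via a 12-lead continuous Holter". This covers the same two days of Cycle 1, Day 1 and Day 15. The QTcF analysis and the exposure-ECG modelling "are documented in a separate analysis plan". In this SAP the Holter data are otherwise only listed (text after Table 5).

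**What feeds the tables.** Section 5.6.5.2 averages triplicates at timepoints given as "screening, predose and post dose on Day 1 of Cycle 1, 2, 3, 4, EOT, unscheduled, etc". This second list names Cycle 1 Day 1 without a phase limit and does not name Day 15.

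**The counting rule.** Subjects meeting a Table 5 criterion "will be summarized (based on worst post-baseline results) and presented by treatment groups". The interpretation shift table also runs from baseline to the worst post-baseline reading.

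**The columns.** Section 5: "grouping by starting dose levels will be applied to all analyses, unless specified otherwise", with subjects from both phases included. Section 5.6.2.1 gives "starting dose levels for Phase 1 subjects (100 mg, 200 mg, 300 mg, 450 mg and 600 mg"). Section 3.2 places Phase 2 at the recommended Phase 2 dose. Its value is redacted in Section 5, but Sections 5.2.4, 5.3.4, 5.4.2 and 13.2 restrict analyses to subjects who started on 450 mg.

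**The concern.** A worst-value count can only stay the same or rise as readings are added. If one dose column holds subjects observed from the first dose, and the others hold subjects whose scheduled 12-lead ECGs start at Cycle 2 Day 1, the columns differ in observation window as well as in dose. A reader comparing QTcF, PR, QRS or heart-rate outliers at 450 mg with those at 600 mg or at the lower doses would be comparing both at once, and the table gives no sign of it.

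The direction is predictable: other things equal, the 450 mg column is raised. The SAP has no rule that limits the table to common timepoints, splits it by phase or brings in Holter-derived Cycle 1 values. Heart rate deserves care in this trial: bradycardia is the one grouped adverse event term that Section 5.6.2.4 defines, and Table 5 has its own criterion for a fall below 40 bpm.

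**Working it through.** The SAP gives no figure on this point, so there is none to reproduce. The check counts scheduled readings and shows what the difference in counts does to a worst-value rate.

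**Step 1. Scheduled post-baseline triplicate timepoints (Section 5.6.5.2)**

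| Timepoint | Phase 2 | Phase 1 |
|---|---|---|
| Cycle 1 Day 1 postdose | 1 | 0 |
| Cycle 1 Day 15 | 1 or 2 | 0 |
| Cycles 2, 3 and 4 Day 1, predose and 3 h postdose | 6 | 6 |
| End of treatment | 1 | 1 |
| Total | 9 or 10 | 7 |

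The Day 15 count is a range because the SAP does not say whether Day 15 has one timepoint or two. Safety follow-up, local and unscheduled ECGs are not counted.

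**Step 2. Chance that a subject is flagged at least once**

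Formula: 1 − (1 − p)^k, for k readings with the same probability p per reading, independent. Both p and independence are assumptions; the SAP gives neither. For a subject followed through Cycle 4 plus end of treatment:

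| p | Phase 2, k = 9 | Phase 2, k = 10 | Phase 1, k = 7 | Ratio |
|---|---|---|---|---|
| 1% | 8.6% | 9.6% | 6.8% | 1.27 to 1.41 |
| 2% | 16.6% | 18.3% | 13.2% | 1.26 to 1.39 |
| 5% | 37.0% | 40.1% | 30.2% | 1.23 to 1.33 |

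**Step 3. Early stoppers, p = 2%**

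- Stops after Cycle 1 Day 15 and before Cycle 2 Day 1, then has the end-of-treatment ECG: 3 or 4 readings against 1, so 5.9% or 7.8% against 2.0%.
- Reaches Cycle 2 Day 1, then end of treatment: 5 or 6 readings against 3, so 9.6% or 11.4% against 5.9%.

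**Step 4. What makes the gap smaller**

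- *Correlation.* Under complete dependence all of a subject's readings exceed the threshold together. Both phases are then at p, and the ratio is 1. The truth lies between 1 and the ratios above.
- *A safety follow-up ECG.* The collection sentence lists none, but Sections 5.6.5.2 and 8 bring that visit into the analysis. If one is taken, each count rises by one. Through Cycle 4 this gives 10 or 11 against 8, or 18.3% or 19.9% against 14.9% at p = 2%. For the Cycle 1 stopper it gives 4 or 5 against 2, or 7.8% or 9.6% against 4.0%.
- *Mixing within the column.* The 450 mg column also holds Phase 1 subjects. If a share w of it is Phase 2, the column excess at p = 2% is w × (16.6 − 13.2) to w × (18.3 − 13.2), that is, w × 3.4 to w × 5.1 percentage points.

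**Step 5. Effect of common timepoints**

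Limited to Cycles 2 to 4 Day 1 plus end of treatment, every column has 7 scheduled readings. At the same p the flag probability is then equal: 6.8%, 13.2% or 30.2% for p of 1%, 2% or 5%.

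**The case against.** **The exclusion of Phase 1 Cycle 1 values is inferred.** The second timepoint list has no phase limit, and the shift-table baseline rule mentions Day 1 predose triplicates without one. The Phase 2 bracket could attach to Day 15 alone. The SAP never says outright that Holter-derived values stay out of Table 5, and the protocol's schedule of assessments, not available here, might settle it. This stands as a reason to ask for a statement, but it does not remove the point. If the bracket covers Day 15 only, the counts are 9 or 10 against 8, which at p = 2% is 16.6% or 18.3% against 14.9%. The imbalance disappears only if Holter-derived values enter for both days, and no sentence provides for that.

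**Other ECGs count too.** Unscheduled ECGs are possible in either phase, so Phase 1 subjects have none scheduled in Cycle 1, which is not the same as none at all. Local ECGs from Cycle 5 make the total depend on time on treatment, which the SAP does not give by dose. This stands, and it is why the direction is stated for equal follow-up.

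**The all-data table is a legitimate safety display.** Dropping observed Cycle 1 readings would be a loss. This stands too, and the fix keeps that table.

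**A stronger reading.** One might infer that the ECG dose-response in this trial is masked or reversed. The documents do not support that. Safety summaries are descriptive, and no between-dose ECG test is specified. The by-timepoint summaries allow Cycles 2 to 4 to be compared visit by visit across doses, and the Phase 1 Holter data have their own plan with exposure-ECG modelling. Distortion is possible in the worst-value tables and is not shown for the study as a whole.

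**Conclusion.** The point holds for Table 5 and the ECG interpretation shift table. On the natural reading of Sections 5.6.5.1 and 5.6.5.2, the worst post-baseline 12-lead ECG is taken over unequal schedules: 9 or 10 scheduled readings through Cycle 4 plus end of treatment for Phase 2 subjects, and 7 for Phase 1 subjects. With equal follow-up and equal true risk, this raises the 450 mg column relative to the Phase 1-only doses.

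The size cannot be fixed from the SAP. The 2% figures are illustrative: they rest on an assumed per-reading probability and independence, they describe a Phase 2 against a Phase 1 subject rather than the mixed column, and correlation reduces them. The relative gap is larger for early stoppers. That Phase 2 subjects all sit in the 450 mg column is inferred from the 450 mg restrictions elsewhere in the SAP.

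The consequence is limited to how these descriptive tables are read across doses. It is still worth correcting, because the direction is predictable and the remedy is cheap.

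**What to change.** In Section 5.6.5.2:

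1. Keep Table 5 on all post-baseline data as the safety display, and split the 450 mg column into Phase 1 and Phase 2.
2. Add a by-dose version restricted to timepoints scheduled in both phases (Cycle 2 Day 1 onward and end of treatment), and use it for comparison across doses. Treat the interpretation shift table the same way, or footnote its unequal schedule.
3. State whether Phase 1 Holter-derived Cycle 1 values enter these tables. Reconcile the two timepoint lists, since the second names Cycle 1 Day 1 without a phase limit and omits Day 15.

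The cost is one extra version of an existing table, a column split and a clarifying sentence, with no new data. The common-timepoint version leaves out Cycle 1 readings, but the all-data table retains them.

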**Table 5 Criteria for Categorical Analysis of ECG Parameters**

ECG parameter	Criteria
QTcF	> 450 and $\leq$ 480 msec
	> 480 and $\leq$ 500 msec
	> 500 msec
	Change from baseline > 30 and $\leq$ 60 msec
	Change from baseline > 60 msec
	> 500 msec or change from baseline > 60 msec
PR	Change-from-baseline > 25% resulting in PR > 200 msec
QRS	Change-from-baseline > 25% resulting in QRS > 120 msec
HR	Changes reflecting a more than 25% decrease from baseline to a HR < 50 bpm
	Changes reflecting a more than 25% decrease from baseline to a HR < 40 bpm
	Changes reflecting a more than 25% increase from baseline to a HR > 100 bpm

HR = heart rate, QTcF = QT interval corrected for heart rate using Fridericia's formula.

Shift tables will present changes in ECG interpretation (categorized as normal; abnormal, not clinically significant; and abnormal, clinically significant) from baseline to worst post-baseline reading; if multiple interpretation records are collected in triplicate on Day 1 predose, the worst interpretation (eg, abnormal is worse than normal) prior to the first dose will be used as baseline interpretation.

All ECG data, including 24 hour continuous Holter ECG, central and local 12-lead ECG data will be listed. All ECG abnormalities based on central/local 12-lead ECG will also be listed.

## 5.6.6 Other Safety Analyses

### 5.6.6.1 Endometrium Safety Sub-Study Assessments

For Phase 2 patients in the Endometrium Safety Evaluable Set, summary statistics at each protocol visit for uterine volume and double endometrial thickness (DET) will be displayed.

Change from baseline at all post-baseline assessments will also be presented, including 2-sided 90% confidence interval for change from baseline in DET.

All endometrium assessment data will be listed.

